8.2. Study Drug Administration

Duration of treatment (days treated) is the number of days on treatment based on the first and last days of treatment with the study drug (last day of study drug – first day of study drug + 1). The last date of study drug for patients who are still ongoing in the study when part A is locked, will be defined as the latest of the following: last neurological evaluation date, last MRI scan date, last date of T25FW, 9HPT, SDMT, CVLT, BVMT, or MSWS, last date of safety evaluation including laboratory, ECG and vital signs data. Weeks on treatment using the categories ≤ 4 week, >4 to ≤ 8 weeks, >8 to ≤ 12 weeks, >12 to ≤ 24 weeks, >24 to ≤ 36 weeks, >36 to ≤ 48 weeks, and >48 weeks will be summarized using descriptive statistics. The last category of >48 weeks specified in the last sentence will include patients with variable treatment duration. In order to define treatment duration in weeks, 7 days will be used as denominator. Duration of treatment (days, weeks and years) will also be summarized using descriptive statistics, including the total number of days/weeks/years. In order to define treatment duration in years 365.25 days will be used as denominator.

In addition for patients who perform an ET visit and continue to come to the off-drug follow-up visits, the off-drug study duration will be presented and will be defined as following: last date in the study-last day of study drug+1. The last date in the study will be taken from the study completion form for patients who withdrew from the study prior to the lock of the part A, while for patients who didn't withdraw prior to the lock of part A, it will be defined as the latest of the following: last neurological evaluation date, last MRI scan date, last date of T25FW, 9HPT, SDMT, CVLT, BVMT, or MSWS, last date of safety evaluation including laboratory, ECG and vital signs data.

All the summaries presented in this section besides categorical week presentation will be repeated to include both part A and part B when the study is completed. Since all the patients will have treatment and study completion forms filled out at the end of the study, those forms will be used for definition of last day of study drug and last date in study respectively.

8.3. Adverse Events

All adverse events (AEs) will be coded using MedDRA. Summaries will be presented for all adverse events (overall and by severity), adverse events determined by the investigator to be treatment-related (overall and by severity), serious adverse events, adverse events causing discontinuation of the study drug, non-serious adverse events, and adverse events by outcome. The AEs will be presented by system organ class and preferred term. Each summary will include number of patients who experienced at least one AE within each category and corresponding percentage from the ST population, number of adverse events within each category and corresponding event rate. For incidence, patients will be counted only once in each system organ

class category and only once in each preferred term category. For frequency in cases when more than one AE with the same preferred term (PT) started on the same date for the same patient, these will be considered as duplicates and will be counted as one AE for that patient. If onset date of AEs with the same PT is partially unknown, then these AEs will be counted as separate AEs. An event rate will be defined as the total number of AEs divided by total exposure to study drug in patient years. Treatment-related adverse event summaries will include adverse events with missing relationship to study drug.

For the summaries by severity, for incidence patients are counted at the greatest severity, and for frequency when cases with duplicate AEs appear, the greatest severity will be assigned for that AE. Adverse events missing the flag indicating serious will be excluded from the summary of serious adverse events but included in the summary of non serious adverse events. For the summary by outcome, for incidence patients are counted at their worst outcome and for frequency when cases with duplicate AEs appear, the worst outcome will be assigned for that AE.

Treatment emergent AEs only which happened under study treatment will be included for all summaries and are defined as events with onset between (including) the date of first study drug dose , up to seven days after the date of last study drug dose. In addition, a summary of all AEs that happened following seven days after the last dose of the study drug will be presented as well.

All analyses presented in the section will be repeated to include both part A and part B when the study is completed.

All AEs will be presented in patient data listings.

Listings for deaths, serious adverse events, and adverse events leading to discontinuation will be presented.

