While laquinimod at the 0.6 mg dose has been extensively studied in RRMS, this is the first study assessing laquinimod in PPMS patients, bridging the 0.6 mg dose experience and assessing a higher dose of 1.5 mg versus placebo.

Note: On 30 December 2015 the Data Monitoring Committee (DMC) for the CONCERTO and ARPEGGIO studies held an unscheduled meeting to review cardiovascular events. The DMC found an imbalance in serious cardiovascular events in the high dose treatment arms (1.2 mg in CONCERTO, 1.5 mg in ARPEGGIO): in CONCERTO there were 6 such cases in the 1.2 mg arm but none in the 0.6 mg or placebo arms, along with a myocardial infarction in the ARPEGGIO 1.5 mg dose group and a cerebral infarction in a 31-year old patient in the 1.2 mg arm of CONCERTO. Due to these events and the DMC recommendation to stop all laquinimod treatment arms above 0.6 mg in the MS trials, the 1.5 mg treatment arm in the ARPEGGIO study was discontinued as of 01 January 2016. The risk/benefit balance of this dose was considered negative at that point.

The DMC did not identify any overt cardiovascular risk in the 0.6 mg treatment arm, but felt that long term monitoring for emergence of any signal is necessary. Therefore, the 0.6 mg treatment arm will be continued while the sponsor closely monitors cardiovascular events in all laquinimod

studies. Additional measures implemented in this protocol amendment include an emphasis on disallowed medications and stopping rules for organ impairment (ie, factors which may increase laquinimod exposure), as well as regular evaluation and management of major modifiable cardiovascular risk factors.

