The DMC did not identify any overt cardiovascular risk in the 0.6 mg treatment arm, but felt that long term monitoring for emergence of any signal was necessary. As of 29 September 2015, 2347 patients had been exposed to laquinimod 0.6 mg for 10,417 patient-years. It is estimated that the rate for myocardial infarction and cardiovascular death for patients treated with laquinimod 0.6 mg is about 0.16 per 100 person-years which is within range of the expected cardiovascular event incidence in the underlying population. Therefore, while no increased risk was seen with laquinimod 0.6 mg, because of the findings with higher doses, there is a potential risk that some individuals may be at increased risk of cardiovascular events while taking laquinimod 0.6 mg. Appropriate risk mitigation procedures have been implemented via a protocol amendment to restrict excess drug exposure due to disallowed medications or organ impairment, as well as to assure evaluation and management of cardiovascular risk factors.

Given the unmet need for treatments of progressive MS, the data supportive of a potential effect of laquinimod in this population, and the identified safety profile of laquinimod, it is judged that the administration of laquinimod to patients with PPMS has the potential to yield clinical benefits which may outweigh the potential risks, supporting investigation of its role in this patient population for which there is equipoise.

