#### **7.1.6. Protocol-Defined Adverse Events for Expedited Reporting**

Ischemic cardiac events (such as myocardial infarction, unstable angina, acute coronary syndrome etc), and cerebrovascular events (such as cerebral arterial occlusion, cerebral ischemia, etc) should be reported to the sponsor within 48 hours, including completion of the corresponding dedicated CRF.

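### The SAP prespecifies no pooled analysis of the protocol-defined ischemic events and counts a missing seriousness flag as non-serious, so any composite 0.6 mg rate would be post hoc

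*SAP*

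**What the plan says.** **The event group.** Protocol 7.1.6 groups ischemic cardiac events (infarction, unstable angina, acute coronary syndrome and the like) with cerebrovascular events. It asks for reporting within 48 hours, "including completion of the corresponding dedicated CRF". Protocol 1.1.1.2 gives the background: the DMC found no overt cardiovascular risk at 0.6 mg but "felt that long term monitoring for emergence of any signal is necessary". Protocol 1.4.2 puts the rate of myocardial infarction and cardiovascular death at 0.6 mg across the programme as one that "is about 0.16 per 100 person-years".

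**The planned AE analysis.** SAP 8.3 states: "AEs will be presented by system organ class and preferred term". Each summary gives patients with at least one event, the percentage, and the "number of adverse events within each category and corresponding event rate". The rate is defined: "An event rate will be defined as the total number of AEs divided by total exposure to study drug in patient years". Summaries are by treatment group (SAP 8.1). All AEs are listed by patient, with further listings for deaths, serious AEs and AEs leading to discontinuation.

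**The output list.** AE tables 15.83 to 15.91 in SAP 13.1 follow the organ class and preferred term layout. No table, listing or graph in SAP 13 is named for the 7.1.6 group or its CRF.

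**Missing flags.** SAP 8.3 says: "Adverse events missing the flag indicating serious will be excluded from the summary of serious adverse events". Those events go to the non-serious table. The same section counts an AE with missing relationship as related.

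**The concern.** After Amendment 02, whether 0.6 mg carries any of the cardiovascular risk seen at higher doses is the main open safety question. The protocol answers it on the data-collection side with a defined group, a reporting clock and a CRF. The SAP has no matching analysis. It was prepared after Amendment 02, recites the DMC findings in section 3.1, and was reopened in June 2017 to add gender analyses, so there was opportunity to add one.

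Two things are at stake. First, a composite whose terms are chosen after unblinding is open to challenge whichever way it falls. Second, a table row showing zero events, with no interval beside it, does not tell the reader how large an excess the data still allow.

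The missing-flag rule is a smaller matter. Two conventions in one section point in opposite directions without a reason, and the less cautious one governs the serious AE table.

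**Working it through.** **1. Does any planned row equal the 7.1.6 group?** No. Protocol Table 3 lists myocardial infarction under cardiac disorders and cerebrovascular accident under nervous system disorders. One organ class row therefore misses part of the group, and each of those rows also contains unrelated events. Adding preferred terms afterwards is possible from the listings, but the choice of terms would be post hoc. Adding row counts could also count a patient twice.

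**2. The plan's own figures.**
- *Arm size.* With 126 per arm, difference 0.3, SD 0.8 and two-sided 5%: 0.3 / (0.8 × √(2/126)) − 1.96 = 1.016, so power is 84.5%, against 84% stated. 252 / 0.9 = 280, or 140 per arm. This reproduces.
- *The 0.16 rate.* Its numerator is not given, so it cannot be reproduced. Over the 10,417 patient-years in Protocol 1.4.2 it implies 0.0016 × 10,417 = 16.7, about 17 events (17 / 10,417 = 0.163 per 100).

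**3. What the trial could show at 0.6 mg.** The documents do not give the arm's exposure. I assume 140 patients followed on average from 48 weeks (the Part A minimum) to 2 years. The exact two-sided 95% Poisson limits for k events in T patient-years are χ²(0.025; 2k)/(2T), or 0 when k = 0, and χ²(0.975; 2k + 2)/(2T). The upper-limit numerators are 3.689 for k = 0 and 5.572 for k = 1. Rates are per 100 patient-years.

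| Assumed mean follow-up | T | Expected events at 0.16 | P(0 events) | Limits, 0 events | Limits, 1 event |
|---|---|---|---|---|---|
| 48 weeks | 140 × 336/365.25 = 128.8 | 0.21 | 81% | 0 to 2.86 | 0.02 to 4.33 |
| 1.5 years | 210 | 0.34 | 71% | 0 to 1.76 | 0.01 to 2.65 |
| 2 years | 280 | 0.45 | 64% | 0 to 1.32 | 0.01 to 1.99 |

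If only 126 patients contribute 48 weeks each, T is 115.9 and the zero-event upper limit is 3.18.

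Against 0.16, the zero-event limits are 1.32/0.16 ≈ 8 to 2.86/0.16 ≈ 18 times higher. This ratio is rough, because 0.16 covers infarction and cardiovascular death while the 7.1.6 group is defined differently and includes unstable angina and cerebrovascular events.

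**4. The missing-flag rule.** Each AE with a blank flag lowers the serious count by one and raises the non-serious count by one. The all-AE table and its rate do not change. The documents give no basis for estimating how many blanks there will be.

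**The case against.** **Rates are already planned.** SAP 8.3 gives counts and patient-year rates for every preferred term and organ class, by arm, for all AEs and for serious AEs, with full listings. A reader might infer that the trial will yield no usable cardiovascular rate at 0.6 mg, or that the events appear only as scattered terms. The documents do not support either reading. What is missing is a prespecified composite with an interval. This objection stands and limits the point to that.

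**Exposure is the real limit.** Fewer than one event is expected under 0.16 per 100 patient-years, and a pooled table would carry the same wide interval. This also stands. It is a reason to print the interval rather than leave a bare zero, but not a claim that regrouping makes the rate informative.

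**Most of the signal lay elsewhere.** Seven of the eight cases the DMC reviewed came from CONCERTO and one from this trial (Protocol 1.4.1.1.7). Monitoring is assigned to the sponsor across all laquinimod studies, with regular DMC review. That is correct, and it keeps the point from being critical. It does not explain collecting a defined group and then not analysing it.

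**The dedicated CRF is incomplete as a source.** It came with Amendment 02, dated 01 February 2016, when 301 patients were already enrolled. A pool drawn from it alone could miss earlier events, including the infarction in the 1.5 mg arm. This stands and shapes the fix.

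**Missing flags should be rare.** Protocol 7.1.2 requires seriousness to be recorded for every AE, and Protocol 13.2 has CRFs checked for mandatory values. A reader might infer that the rule could hide an infarction. It could not: the event would remain in the all-AE tables and listings.

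**Conclusion.** The point holds in limited form. SAP 8.3 and SAP 13 contain no pooled analysis of the group that Protocol 7.1.6 defines. The planned rates, by organ class and preferred term, carry no interval, and the group spans at least two organ classes. A composite 0.6 mg rate would therefore be post hoc.

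The size is best stated as precision. With zero events, the exact upper limit is about 1.3 to 2.9 per 100 patient-years, resting on the assumed 280 to 129 patient-years. The comparison with 0.16 is approximate only, and it is no evidence that an excess exists.

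The missing-seriousness rule is inconsistent with the rule for missing relationship and is the less cautious of the two, but its practical effect is probably small. Both changes are worth making because they are cheap. Neither alters an efficacy analysis or makes the cardiovascular rate precise.

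**What to change.** - **Term list.** Before unblinding, fix a MedDRA list for the 7.1.6 group and apply it to all coded AEs from first dose. Use the dedicated CRF as a supplement, not as the sole source.
- **Table.** Add one table to SAP 8.3 and SAP 13.1 with rows for ischemic cardiac, cerebrovascular, and either. For each arm give patients with an event, patient-years to first event, and the rate per 100 patient-years with exact 95% CI. Add the 0.6 mg minus placebo difference. The 1.5 mg arm stays descriptive, as SAP 5.1 requires.
- **Listing.** Add one listing of the events in this group to SAP 13.2.
- **Missing seriousness.** Query blank flags before lock and count any still unresolved as serious.

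The cost is one table, one listing and the term list. Coded AEs are already collected, so no new data collection is needed. The serious AE count may rise slightly.

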Patients who are discontinued from study treatment will be encouraged to continue all scheduled visits and procedures after study drug discontinuation (with the exception of procedures associated with drug dispensing and accountability, pregnancy testing, and pharmacokinetic sampling).

a An unscheduled visit may be performed at any time at the patient's request or per investigator's discretion. Only mandatory procedures are specified; additional assessments per clinical discretion. In addition, unscheduled urgent safety laboratory samples, pharmacokinetic blood samples, and/or samples for potential biomarker analyses may be collected at the discretion of the investigator or medical monitor at any time to assist with further investigations of cardiovascular events or other clinical event of interest. The samples should be collected as soon as possible in association with the event.

b For the purpose of scheduling study visits, a week is defined as 7±2 days.

c In addition, an evaluation should take place as soon as possible for patients already in the study, following approval of Global Amendment 2.

d Vital signs include temperature, pulse and blood pressure. Height will be measured at screening visit. Weight will be measured at all visits. At baseline (week 0), pulse and blood pressure will be measured pre dose as well as 30 and 60 minutes after onsite drug administration.

e At baseline (week 0), 3 ECG recordings 10 minutes apart are required before first dose.

f Chest X-ray can be omitted if the report of a chest X-ray performed within 24 weeks of screening is obtained, or if a screening chest X-ray is considered unacceptable per local regulations.

g Anemia panel includes blood smear, serum iron, ferritin, total iron binding capacity, folic acid, haptoglobin, IL-1, IL-6, IFN- $\gamma$ , TNF- $\alpha$ , and hepcidin. Assessed at baseline and also at 1 subsequent time point (with B12) if hemoglobin decrease of >1 g/dL from the patient's hemoglobin level at baseline and the decrease is confirmed.

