### **7.1.2. Recording and Reporting Adverse Events**

For adverse event recording, the study period is defined for each patient as that time period from signature of the informed consent form through the end of the follow-up period. For this study, the follow-up period is defined as 30 days after the last dose of study drug.

All adverse events that occur during the defined study period must be recorded on the source documentation and transcribed onto the CRF, regardless of the severity of the event or judged relationship to the study drug. For serious adverse events, the Serious Adverse Event Form must also be completed and the serious adverse event must be reported immediately (see Section [7.1.5.3.1](#)).

At each contact with the patient, the investigator or designee must query the patient for adverse events by asking an open-ended question such as, "Have you had any unusual symptoms or medical problems since the last visit? If yes, please describe." All reported or observed signs and symptoms will be recorded individually, except when considered manifestations of a medical condition or disease state. A precise diagnosis will be recorded whenever possible. When such a diagnosis is made, all related signs, symptoms, and any test findings will be recorded collectively as a single diagnosis on the CRF and, if it is a serious adverse event, on the Serious Adverse Event Form.

The clinical course of each adverse event will be monitored at suitable intervals until resolved or stabilized or returned to baseline, or until the patient is referred to the care of a health care professional, or until a determination of a cause unrelated to the study drug or study procedure is made.

Placebo-Controlled Study – Multiple Sclerosis  
Clinical Study Protocol with Global Amendment 02 Study TV5600-CNS-20006 (ARPEGGIO)

The onset and end dates, duration (in case of adverse event duration of less than 24 hours), action taken regarding study drug, treatment administered, and outcome for each adverse event must be recorded on the source documentation and transcribed onto the CRF.

The relationship of each adverse event to study drug treatment and study procedures, and the severity and seriousness of each adverse event, as judged by the investigator, must be recorded as described below.

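### Table 15.91 has no off-drug denominator, so adverse events after stopping drug fall on on-drug exposure, and the protocol gives two recording periods for them

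*SAP*

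**What the plan says.** **Denominators.** SAP 8.3 says that each AE summary carries a patient count with a percentage of the safety (ST) population, and the "number of adverse events within each category and corresponding event rate". The only rate it defines is: "An event rate will be defined as the total number of AEs divided by total exposure to study drug in patient years". Treatment-emergent events run from first dose "up to seven days after the date of last study drug dose". The section then adds that "a summary of all AEs that happened following seven days after the last dose of the study drug will be presented as well". This is Table 15.91.1 (Part A) and 15.91.2 (Part B), by treatment group, on the safety population.

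**Off-drug time.** SAP 8.2 covers patients who have an early termination (ET) visit and keep attending. For them, "the off-drug study duration will be presented and will be defined as following: last date in the study-last day of study drug+1". Table 15.82 reports this by arm. SAP 8.3 does not use it.

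**Recording.** Protocol 7.1.2 closes the AE recording period as follows: "For this study, the follow-up period is defined as 30 days after the last dose of study drug". The notes to Table 5 say: "Patients who are discontinued from study treatment will be encouraged to continue all scheduled visits and procedures after study drug discontinuation". The notes to Table 6 and Section 3.6.7 say the same. The listed exceptions are drug dispensing and accountability, pregnancy testing and pharmacokinetic sampling, to which Section 3.11.3 adds GFR testing. AE recording is not an exception, and the synopsis has AEs recorded at every visit.

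**The concern.** An AE that starts more than a week after the last dose can occur only in someone who has stopped, during time off drug. Dividing it by time on drug gives a ratio of two unrelated quantities. The error is (off-drug time)/(on-drug time), and that fraction differs greatly between an arm stopped early as a whole and arms where few patients stop. The percentage has the same fault, because its denominator includes patients who were never at risk of an off-drug event.

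The table matters because SAP 5.1 removes data after discontinuation from the safety analyses, except to identify later AEs. Table 15.91 is therefore the planned tabulation of off-drug events. The 1.5 mg arm was stopped over serious cardiovascular events in the high-dose arms, for which Protocol 1.4.1.1.7 reports no known mechanism and no specific time-to-event pattern. A reader will look at this table for that arm.

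The recording conflict adds a second problem: how many events reach the numerator after day 30 depends on which protocol passage a site follows.

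**Working it through.** The documents state no off-drug rate or off-drug person-time, so there is no plan figure to reproduce. Two consistency checks on the inputs pass: 286/3 = 95.3, against 95 randomised to 1.5 mg; and (375 − 95)/2 = 140 per continuing arm.

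**Formula.** Printed rate / true off-drug rate = (events / on-drug PY) / (events / off-drug PY) = off-drug PY / on-drug PY, where PY is patient-years.

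**Inputs from the documents**
- 35 PY in 191 individuals at 15 November 2015 (Protocol 1.4.1.1.7)
- 95 patients randomised to 1.5 mg (SAP 3.1), arm discontinued as of 01 January 2016
- 140 patients per continuing arm (SAP 3.3)
- 10% anticipated dropout (Protocol 9.2)

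**Assumptions**
- The 35 PY are shared equally by three arms, with linear accrual over the 47 days to 01 January 2016.
- All 95 patients contribute off-drug time in the 30-day case.
- Retention is 25-100% in the all-visits case.
- Off-drug follow-up is 0.92 years (48 weeks) to 1.27 years (8 January 2016 to an assumed Part A end in mid-April 2017).
- In a continuing arm, 10% stop drug midway through 48 weeks.

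**1.5 mg, on drug**
- To 15 November 2015: 35/3 = 11.7 PY
- Patients already enrolled: (191/3) × 47/365.25 = 8.2 PY
- Later entrants: (95 − 63.7) × 23.5/365.25 = 2.0 PY
- Total: about 21.9 PY

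**1.5 mg, off drug**
- Recording stops at day 30 (days 8-30, 23 days): 95 × 23/365.25 = 6.0 PY. Factor 6.0/21.9 = 0.27.
- All visits, 25% stay, 0.92 years: 0.25 × 95 × 0.92 = 21.9 PY. Factor 1.0.
- All visits, 100% stay, 0.92 years: 95 × 0.92 = 87.4 PY. Factor 4.0.
- All visits, 100% stay, 1.27 years: 95 × 1.27 = 120.7 PY. Factor 5.5.

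**Continuing arm (140 patients, 14 stopping)**
- On drug: 126 × 0.92 + 14 × 0.46 = 122.4 PY
- Off drug, 30-day recording: 14 × 23/365.25 = 0.88 PY. Factor 0.88/122.4 = 0.007.
- Off drug, all visits and all 14 staying: 14 × 0.46 = 6.4 PY. Factor 6.4/122.4 = 0.05.

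So the direction of the 1.5 mg error is not fixed, while the continuing-arm rate is too low in both cases.

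**Percentage.** With 14 of 140 stopping, a percentage of the safety population is 14/140 = one tenth of the percentage among those who stopped. In the 1.5 mg arm, where everyone stopped, the two coincide, apart from patients no longer followed.

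**Recording windows.** The SAP's seven days and the protocol's 30 days do not conflict: the first is an analysis cut-off, the second a collection limit. The conflict lies within the protocol, between the 30 days of Section 7.1.2 and the continued visits of Section 3.6.7, the synopsis and Tables 5 and 6.

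**The case against.** **The rate rule may not reach this table.** In SAP 8.3 the sentence on what each summary includes follows a list that does not name the post-drug summary. That summary is added later with no format stated. This is a fair reading. On it, Table 15.91 has no denominator at all, and the same sentence is still needed.

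**A reader might infer that the off-drug safety of the 1.5 mg arm cannot be read.** The documents do not support that. Event counts, listings of all AEs, serious AEs and deaths, and death narratives are planned, and Table 15.82 gives off-drug duration by arm. The arm is descriptive only, so no inferential comparison is at stake. What fails is the rates and percentages in Table 15.91.

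**A reader might infer that the 1.5 mg rate is inflated, or that off-drug time is most of that arm's safety time.** Both depend on retention and on the recording window. The protocol only encourages continued attendance and gives no retention figure; under 30-day recording the rate is too low. A specific between-arm distortion ratio would stack these same assumptions, so none is claimed.

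**A reader might infer that some sites would record nothing after day 30.** That goes too far. Section 7.1.2 itself requires an AE query at each contact, Section 7.1.5.3.1 asks for later serious events the investigator learns of, and Section 7.1.6 requires ischaemic cardiac and cerebrovascular events to be reported within 48 hours and states no 30-day limit. The gap is mainly in non-serious events.

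**Conclusion.** Two defects stand.

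First, followed as written, SAP 8.3 divides off-drug events by on-drug exposure and by the whole safety population. The Table 15.91 rates and percentages are then not interpretable, least of all between the 1.5 mg arm and the continuing arms. For 1.5 mg the printed rate could lie anywhere from about 0.27 to about 5.5 times the true off-drug rate. In a continuing arm it would be about 0.007 to 0.05 times the true rate. The need for a different denominator follows from the text alone. The sizes rest on assumed retention, follow-up length, equal exposure across arms and 10% stopping midway.

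Second, the protocol gives two AE recording periods for patients who stop drug and stay in follow-up. Completeness after day 30, chiefly for non-serious AEs, therefore depends on the site's reading. This affects the counts as well as the rates, and a better denominator alone does not cure it.

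**What to change.** **SAP 8.3, Table 15.91 (Parts A and B).** Take percentages from all patients who stopped study drug and are at risk beyond day 7. Take rates from their off-drug patient-years, counted from day 8 after last dose to the end of AE collection or last contact, whichever is first. Report the number followed.

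The SAP 8.2 duration cannot be used unchanged. It starts at the last dose and covers only patients with an ET visit who keep attending, whereas the numerator takes every post-drug AE. Extend it to everyone who stopped, so that numerator and denominator describe the same patients and time.

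**Protocol.** Reconcile Section 7.1.2 with Section 3.6.7, the synopsis and Tables 5 and 6, so that one AE recording period applies to patients who stop drug and remain in follow-up.

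**Cost.** A small derivation change; a short protocol amendment, which under Section 11.1.1 generally needs ethics committee approval; and, if the longer period is adopted, somewhat more AE recording at visits already held.
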